1.0 Objectives

Primary Objective:

To evaluate the effect of Rolapitant on nausea/vomiting in patients with sarcoma receiving multi-day HEC regimen of Doxorubicin and Ifosfamide (AI).

Secondary Objectives:

- (1) To evaluate the toxicity of Rolapitant in patients receiving AI regimen.
- (2) To evaluate the effects of Rolapitant on patient reported outcomes.

2.0 Background

2.1 Chemotherapy-induced Nausea and Vomiting (CINV)

Nausea and vomiting are one of the most debilitating side effects of cytotoxic chemotherapy. CINV is a frequent adverse event that can impair the quality of life in cancer patients (1, 2). The time course of CINV is well recognized for single-day chemotherapy regimens. It may persist for several days and has frequently been classified as having an acute phase (starting within 24 hours of the chemotherapy administration) and a delayed phase (starting approximately 16-24 hours after initiation of chemotherapy and lasting to approximately 120 hours post-chemotherapy). There are both acute (0 to 24 hours) and delayed phases of CINV which are distinct after HEC but less differentiated after MEC. Active management of CINV reduces patient suffering and increases the likelihood that cancer patients will continue to receive potentially life-saving treatment at appropriate doses.

2.2 Prevention/Treatment for CINV

CINV is triggered by multiple factors involving patients' characteristics and type of chemotherapy regimen. Several neurotransmitters, located in the gastrointestinal (GI) tract or in the central nervous system (CNS), are involved with the pathophysiology of CINV, triggering the emetic center located in the medulla (3). These include histamine, acetylcholine, serotonin, dopamine, and substance P (4-7). The acute phase, the first 24 hrs following chemotherapy treatment, is mediated largely by chemotherapy-induced increases in serotonin (5-HT3) release and activation of 5-HT3 receptors on vagal afferent neurons in the gut. 5-HT3 receptor antagonists (5-HT3RA) are clinically effective in preventing acute CINV, particularly when given in combination with corticosteroids such as dexamethasone (8).

Delayed CINV occurs from 2 to 5 days after chemotherapy and has a different etiology than acute CINV (9). Antiemetic therapy with a corticosteroid and 5-HT3RA, particularly with the first generation 5-HT3RA, is less effective during the delayed as compared to

the acute phase of CINV. The primary etiology of delayed CINV appears to involve the release of the neurokinin peptide substance P in the brainstem. When an NK1 antagonist, 5-HT3RA, and corticosteroid are given in combination, there is a greater reduction in CINV compared to that seen with the use of the combination of a 5-HT3RA antagonist and corticosteroid alone. The NK1 receptor antagonist aprepitant was approved by the FDA and by the EMA for the prevention of acute and delayed CINV associated with HEC, including high-dose cisplatin, and MEC when used in combination with a 5-HT3RA and corticosteroids (10). Although aprepitant and fosaprepitant (iv formulation) are effective, dosage adjustment of other concomitantly administered drugs is necessary because aprepitant is a mixed inducer/inhibitor of cytochrome P450 (CYP) 3A4 and also affects other CYP enzymes. Furthermore, aprepitant requires several doses during each cycle of chemotherapy (11-14).

2.3 CINV in Sarcoma Patients Receiving AI regimen

Al is multi-day regimen of highly emetogenic chemotherapy, with high incidence of delayed CINV. Fosaprepitant, NK1 receptor antagonist (RA), administered IV as single dose is FDA-approved, in combination with 5HT3RA and dexamethasone has improved the control of emesis. However, delayed N/V still remains problematic (9). We, therefore investigated the effects of fosaprepitant administered IV on day 1 vs days 1 and 4 on CINV and the effect on ifosfamide (Ifex) and its active metabolites, due to potential drug interactions via CYP450. Patients planned to receive AI, were randomized 1:1 to Arm A (single- dose fosaprepitant on day 1) or Arm B (2-doses, on days 1 and 4). Blood samples were drawn for levels of Ifex/metabolites to be analyzed at the end of study. All patients could receive 2 doses during cycles 3-6. Pts were monitored for N/V with daily symptom diary and FLIE (functional living index -- emesis) score (days 1, 5 and 10). 40 eligible pts were randomized. Fosaprepitant administered as 2 doses resulted in significantly better control of delayed N/V as compared to singledose or the control cycle (response rate 10% and 17% vs 50%, respectively) (15, 16). Fosaprepitant had minor effects on lfex and metabolites levels, which was partly compensated by autoinduction.

2.4 Rolapitant, A New NK-1 Receptor Antagonist

Rolapitant (formerly referred to as SCH 619734) is a potent, selective, competitive neurokinin-1 (NK1) receptor antagonist with no known activity at other pharmacologic targets (17). It binds with high affinity to the human NK1 receptor (Ki = 0.66 nM) and competitively antagonizes functional effects mediated by activation of the NK1 receptor in cultured cells (Kb = 0.45 nM). The endogenous activator of NK1 receptors is the neuropeptide Substance P (18). Rolapitant does not have significant affinity for NK2 or NK3 receptors or for a battery of other receptors, transporters, enzymes, and ion channels. The compound is active in animal models of CINV and has demonstrated efficacy in Phase 2 studies in patients receiving HEC. Rolapitant has been free of clinically relevant drug interactions in studies conducted to date, has rapid and good brain penetration which may contribute to its quick onset of action, and a long half-life that allows for dosing only once during each cycle of chemotherapy. PET occupancy studies as well as clinical efficacy data support the use of only a single dose of rolapitant to protect patients for 5 days from CINV (19, 20).

2.4.1 Preclinical Studies

Rolapitant has been evaluated in a series of non-clinical toxicity studies of up to 6 months duration in rats and up to 9 months duration in monkeys by oral administration and up to 14 days duration in rats and up to 1 month duration in monkeys by intravenous (IV) infusion. Developmental and reproductive toxicity studies, genetic toxicity studies, and safety pharmacology studies were also conducted. In addition, genetic toxicity studies and a safety pharmacology study were conducted with the pharmacologically active metabolite SCH 720881 (M19). Furthermore, 2-year oral carcinogenicity studies of rolapitant in rats and mice have been completed.

The major findings in the non-clinical toxicity studies reported to date are convulsions in rats, mice, and monkeys at high lethal or near lethal doses (oral administration) and in monkeys (after IV infusion) as well as developmental and reproductive findings in female rats. For convulsions, exposure margins have been identified in the non-clinical species relative to clinical exposure data at an oral dose of 180 mg and there has been no evidence of treatment-related seizures in the completed clinical trials. Since the rolapitant clinical development program has not nor will include women who are pregnant or attempting to become pregnant, the findings in the developmental and reproductive studies in rats are not considered relevant for the clinical trials in CINV. The mouse carcinogenicity study with rolapitant was negative; the rat carcinogenicity study showed a non-significant increase in thyroid follicular cell tumors and benign adrenal medullary tumors.

To evaluate the IV administration of rolapitant in humans, blood compatibility and local tolerance studies were also performed. The results from the in vitro blood compatibility study as well as animal studies indicate that the intended clinical formulation does not cause hemolysis in human, rat or monkey blood. The local tolerance study showed that the intended formulation is well tolerated when administered by either the intended IV route or potential misdose routes. Additionally, results obtained from the 14-day IV rat, 14-day IV monkey and one-month IV monkey studies indicate rolapitant is well tolerated at 20 mg/kg/day in rats and up to 15 mg/kg/day in monkeys. These results also indicated that the solubilizing agents in the rolapitant IV formulation are well tolerated at 10 mL/kg when administered at the defined concentration, approximately 5-fold higher than the maximal infusion volume (1.58 mL/kg, 95 mL/60 kg human) anticipated clinically.

2.4.2 In vivo Activity of Rolapitant

Ferrets have proven to be a useful animal model of chemotherapy-induced emesis, and have been used extensively to demonstrate the antiemetic effects of drugs, including NK1 receptor antagonists like aprepitant. Rolapitant produced a dose-dependent inhibition of retching and vomiting with an ED50 of 0.07 mg/kg when dosed orally to ferrets 4 hrs prior to cisplatin treatment. Moreover, a single 1 mg/kg oral dose of rolapitant given 4 hrs prior to cisplatin substantially inhibited both the acute and delayed retching and vomiting for 72 hrs. Cisplatin-induced retching and vomiting was also

completely abolished (ca. >95%) by once daily oral administration of 1 mg/kg of rolapitant for 3 days after cisplatin treatment.

In conclusion, the IV and oral monkey studies have shown that the safety profile of rolapitant is similar at the NOAEL/maximum tolerated dose following administration of rolapitant by either the IV or oral route of administration. Moreover, the systemic toxicity profiles and exposure levels are comparable between IV and oral administrations at these dose levels.

2.4.3 Clinical Experience

The total number of subjects exposed to oral rolapitant is approximately 2,800, which includes 1,567 CINV patients and 1,231 healthy volunteers or patients from several additional Phase 1 and Phase 2 studies (21). Rolapitant was well tolerated at single doses up to 800 mg or as a once-daily dose up to 50 mg for 10 days. Orally administered rolapitant was completely bioavailable, rapidly absorbed, and slowly cleared. Maximum concentrations of a 200 mg dose were approximately 1000 ng/mL and were achieved by approximately 4 hrs. The half-life was approximately 170 hrs (average), suggesting that a single dose may be sufficient to prevent CINV during both the acute and delayed phases of CINV. Rolapitant is highly bound to plasma proteins, with an unbound (free) fraction of <1%. Urinary excretion of the dose is minor, and the major route of elimination is via the feces. Rolapitant is extensively metabolized by oxidation, primarily to M19, an equipotent human NK1 receptor antagonist. The formation and elimination of M19 are slow.

In Phase 1 drug interaction studies, administration of rolapitant did not alter the pharmacokinetics of midazolam, dexamethasone or ondansetron, drugs metabolized by cytochrome P450 3A4. This indicates lack of a clinically relevant inhibition of CYP3A4 by rolapitant. Moreover, the PK of repeated doses of dexamethasone was also unaffected by a single 200 mg (equivalent to the 180 mg free base dose in the treatment section) oral dose of rolapitant, indicating a lack of significant CYP3A4 induction by rolapitant or its metabolite. Inhibition of CYP3A4 by concomitant agents is unlikely to affect the PK of single doses of rolapitant, since concentrations of both rolapitant and the active metabolite M19 were unaffected by repeated daily oral doses (400 mg) of the potent CYP3A4 inhibitor ketoconazole.

In a recently conducted drug interaction study to assess the effect of rolapitant on the pharmacokinetics of specific probe substrates, preliminary results indicate that rolapitant increased the PK exposure of dextromethorphan, a CYP2D6 substrate, digoxin, a P-gp substrate, and sulfasalazine, a BCRP substrate suggesting that rolapitant is a moderate inhibitor of CYP2D6 and an inhibitor of P-gp and BCRP. Therefore, dosage adjustments may be warranted for sensitive CY2D6 substrates and/or P-gp, BCRP transporter substrates when given concomitantly with rolapitant. However, Rolapitant did not alter the

pharmacokinetics of tolbutamide, omeprazole, efavirenz or repaglinide, drugs metabolized by CYP2C9, CYP2C19, CYP2B6, or CYP2C8 respectively. In a recently conducted PK study in subjects with impaired hepatic function, preliminary results indicate comparable rolapitant PK profiles were observed in subjects with mild hepatic impairment and a slight decrease in exposure with subjects with moderate hepatic impairment when compared to healthy subjects. Therefore, dose adjustment for rolapitant when administered to patients with mild to moderate hepatic impairment is not required. Subjects with severe hepatic impairment were not evaluated in this study.

A human ECG study demonstrated no effects of rolapitant 200 mg or 800 mg (4 times the therapeutic dose) on the QTc interval. A clinical PET study demonstrated that single oral doses of rolapitant ranging from 5 to 200 mg can block the occupancy of cortical NK1 receptors by the selective PET ligand 11C-GR205171. After a 200 mg dose, over 90% of central NK1 receptors remained blocked for at least 5 days.

The results from the dose range-finding study showed rolapitant administered as a single dose of 200 mg with a 5-HT3 receptor antagonist and dexamethasone to be highly effective in the prevention of CINV following HEC, together with data from the Phase 1 PET study, led to the dose selection and design of three global multicenter, randomized, parallel-group, double-blind, active-controlled Phase 3 studies conducted in subjects receiving HEC (P04832 and Study P04833) and in subjects receiving MEC (Study P04834).

These studies were designed to evaluate the efficacy of a single dose of rolapitant 200 mg administered orally with granisetron and dexamethasone compared to placebo administered with granisetron and dexamethasone for the prevention of delayed phase CINV (>24 to 120 hours). The primary endpoint of all three studies was achieved (21-24). Specifically, the proportion of subjects who had no emesis and no use of rescue medication during the delayed phase of CINV, >24 through 120 hours following initiation of HEC or MEC, was significantly higher for subjects receiving rolapitant compared with subjects receiving placebo (71.4% vs. 60.9%, respectively, p < 0.001). Likewise, the proportion of subjects who had no emesis and no use of rescue medication was significantly higher for subjects receiving rolapitant compared with subjects receiving placebo during the acute phase (< 24 hours) (83.5% vs. 78.7%, respectively, p = 0.003) and during the overall phase (0-120 hours) (68.7% vs. 58.1%, respectively, p < 0.001). Multiple secondary and tertiary endpoint comparisons favored the rolapitant group in the individual studies and in the pooled analyses and contribute additional support for the benefit of rolapitant during the delayed, acute and overall at risk period (0 to 120 hours) for patients receiving emetogenic chemotherapy. In addition, rolapitant was safe and well tolerated. No AEs were clearly attributable to administration of rolapitant, and neurological and other clinical and laboratory examinations did not detect specific safety signals that could be ascribed to rolapitant.

2.4.4 Drug Interaction

2.4.4.1 Effect of Rolapitant on Other Drugs

Rolapitant is not an inhibitor nor an inducer of CYP3A4. Therefore, no dosage adjustment for dexamethasone (CYP3A4 substrate) is needed when co-administered (25).

Rolapitant is a moderate CYP2D6 inhibitor, an inhibitor of Breast-Cancer-Resistance Protein (BCRP) and an inhibitor of P-glycoprotein (P-gp).

CYP2D6 Substrates with a Narrow Therapeutic Index: Increased plasma concentration of CYP2D6 substrates may result in potential adverse reactions. A three-fold increase in the exposure of dextromethorphan, a CYP2D6 substrate, was observed 7 days after a single dose of Rolapitant. The duration of CYP2D6 inhibition was not studied beyond 7 days and may last longer. Concomitant use with thioridazine is contraindicated. Avoid use of Rolapitant with pimozide. Monitor for adverse reactions if concomitant use with CYP2D6 substrates with a narrow therapeutic index cannot be avoided (25).

BCRP Substrates with a Narrow Therapeutic Index (e.g., methotrexate, topotecan, or irinotecan): Increased plasma concentrations of BCRP substrates may result in potential adverse reactions. Monitor for adverse reactions related to the concomitant drug if use of Rolapitant cannot be avoided. Use the lowest effective dose of rosuvastatin.

P-gp Substrates with a Narrow Therapeutic Index: Increased plasma concentrations of digoxin, or other P-gp substrates, may result in potential adverse reactions. Monitor for increased digoxin concentrations. Monitor for adverse reactions if concomitant use of Rolapitant with other P-gp substrates with a narrow therapeutic index cannot be avoided (25).

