2.4.4.2 Effect of Other Drugs on Rolapitant

Strong CYP3A4 Inducers (e.g., rifampin): significantly reduced plasma concentrations of rolapitant can decrease the efficacy of Rolapitant; avoid use of Rolapitant in patients who require chronic administration of such drugs (25).

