2.4.5 Rationale for the Study

The NK1 antagonist aprepitant was approved by the FDA and by the EMA for the prevention of acute and delayed CINV associated with HEC, including high-dose cisplatin, and moderately emetogenic chemotherapy (MEC) when used in combination with a 5-HT3 antagonist and corticosteroid. Although aprepitant is effective, dosage adjustment of concomitantly administered drugs is necessary because aprepitant is a mixed inducer/inhibitor of cytochrome P450 (CYP) 3A4 and also affects other CYP enzymes. Furthermore, aprepitant requires several doses during each cycle of chemotherapy. Rolapitant has been free of clinically

relevant drug interactions in studies conducted to date, has rapid and good brain penetration which may contribute to its quick onset of action, and a long half-life that allows for dosing only once during each cycle of chemotherapy. PET occupancy studies as well as clinical efficacy data support the use of only a single dose of rolapitant to protect patients for 5 days from CINV. Al is a highly emetogenic regimen with the potential for improvement in delayed nausea/vomiting with rolapitant in addition to 5HT3RA and steroids.

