4.0 Patient Eligibility

Inclusion Criteria

- Patients with sarcoma which is locally advanced, at high risk for relapse or metastatic for whom treatment with doxorubicin plus ifosfamide (AI) or AI and vincristine (VAI) is indicated.
- Must be 18 to 65 years of age.
- Patient must have an estimated life expectancy ≥ 4 months in the opinion of the investigators.
- Male and Females of child bearing potential must use acceptable methods of birth control which include oral contraceptives, spermicide with either a condom, diaphragm or cervical cap, us of a intrauterine device (IUD) or abstinence.
 - Female patients must have a negative pregnancy test at Screening
 - Female patients of childbearing potential must agree to use an acceptable method of birth control (excluding hormonal birth control methods) for 72

hours prior to admission and to continue its use during the study and for at least 30 days after the final dose

- Male patients must agree to use an acceptable form of birth control from study Day 1 through at least 30 days after the final dose
- Adequate hematologic (ANC > 1500/mm³, platelet count > 100,000/mm³), renal (serum creatinine < 1.5mg/dL), hepatic [serum bilirubin count < 1.5 x upper limit normal (ULN) and SGOT or SGPT < 2.5 x ULN, for subjects with known liver metastases < 5 x ULN] functions.
- Karnofsky Performance Status > 60%. (Appendix D)
- Signed informed consent form.
- Patients are required to read and understand English to comply with protocol requirements.

Exclusion Criteria

- a. Any current treatment, medical history, or uncontrolled condition, other than malignancy, (e.g., alcoholism or signs of alcohol abuse, seizure disorder, medical or psychiatric condition) that, in the opinion of the investigator, would confound the results of the study or pose any unwarranted risk in administering study drug to the subject
- b. Patient has a known hypersensitivity to the administration of any prescribed oral or intravenous study medication or metabolite, including but not limited to, a history of hypersensitivity to the drugs or their components, severe renal impairment, severe bone marrow suppression, or systemic infection
- c. Patient is a woman with a positive urine or serum pregnancy test within 3 days prior to study drug administration, is breast-feeding, or is planning to conceive children within the projected duration of the study treatment

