- d. Patient has taken the anti-emetic agents within the last 48 hours prior to the start of treatment with study drug:
 - 5-HT₃ antagonists (ondansetron, granisetron, dolasetron, tropisetron, etc.). Palonosetron is not permitted within 7 days prior to administration of investigational product
 - Phenothiazines (prochlorperazine, fluphenazine, perphenazine, thiethylperazine, chlorpromazine, etc.)
 - Benzamides (metoclopramide, alizapride, etc.)
 - Domperidone
 - Cannabinoids
 - NK1 antagonist (aprepitant)
 - Benzodiazepines (lorazepam, alprazolam, etc)
 - herbal medications or preparations in doses designed to ameliorate nausea or emesis
- e. Patient has received systemic corticosteroids or sedative antihistamines (dimenhydrinate, diphenhydramine, etc.) within 72 hours of Day 1 of the study except

as premedication for chemotherapy (e.g., taxanes). Subjects who are receiving inhaled steroids for respiratory conditions or topical steroids for skin disorders can be enrolled

- f. Patient has symptomatic primary or metastatic CNS disease
- g. Patient has ongoing vomiting, retching, dry heaves, or clinically significant nausea caused by any etiology, or has had such symptoms within 24 hours prior to the start of Day 1 of the study intervention, or has a history of anticipatory nausea and vomiting
- h. Patient must not have been dosed with test drug or blinded study drug in another investigational study within 30 days or 5 half-lives of the biologic activity of the test drug, whichever is longer, before the time of first study dose
- i. Patient who is participating in any investigational agent that is not FDA-approved.
- j. Patient has uncontrolled angina, congestive heart failure (New York Heart Association > class II or known ejection fraction < 40%), uncontrolled cardiac arrhythmia or hypertension, or acute myocardial infarction within 3 months.
- k. Prior surgery or radiotherapy (RT) within 2 weeks of study entry.
- I. Psychological, social, familial, or geographical reasons that would prevent scheduled visits and follow-up.

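### The drug restrictions stated in Section 2.4.4 are not carried into the eligibility criteria (4.0) or the concomitant-medication text (5.1), and Sections 2.4 and 2.4.5 contradict them

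*Combined protocol and SAP*

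**What the plan says.** **The restrictions.** Section 2.4.4.1 states: "Concomitant use with thioridazine is contraindicated. Avoid use of Rolapitant with pimozide". On timing it reports a three-fold rise in exposure to a CYP2D6 substrate 7 days after a single dose, and then says "The duration of CYP2D6 inhibition was not studied beyond 7 days and may last longer". Section 2.4.4.2, on strong CYP3A4 inducers, says that "significantly reduced plasma concentrations of rolapitant can decrease the efficacy of Rolapitant" and tells the reader to "avoid use of Rolapitant in patients who require chronic administration of such drugs".

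**The operative rules.** Section 4.0 names none of thioridazine, pimozide, rifampin, CYP3A4 inducers as a class, or CYP2D6 substrates as a class. Two exclusions come near:

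- Exclusion (a) covers "Any current treatment, medical history, or uncontrolled condition, other than malignancy" that, in the investigator's opinion, "would confound the results of the study or pose any unwarranted risk in administering study drug to the subject".
- Exclusion (d) begins "Patient has taken the anti-emetic agents within the last 48 hours prior to the start of treatment with study drug". It includes an open-ended phenothiazine entry that does not name thioridazine.

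The part of Section 5.1 on breakthrough symptoms and concomitant medication lists four agents that may be taken for breakthrough nausea. It prohibits nothing.

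**The general description.** Sections 2.4 and 2.4.5 both state that studies to date have shown no drug interaction of clinical importance.

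**The concern.** Sites screen and treat patients from Sections 4.0 and 5.1. A restriction that appears only in the background is easily missed. If it is missed, a patient could receive a combination that the same protocol calls contraindicated, and that matters even if it happens once.

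The only route to exclusion is the investigator's judgement under exclusion (a), and two background sections tell the investigator that there is nothing important to look for.

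There is also a lesser statistical side. A patient on a chronic strong inducer may have low rolapitant levels, and would still count towards the complete response (CR) rate in Part I or Arm A. That would pull the rolapitant rate down.

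**Working it through.** **Step 1. Sections set side by side.**

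| Drug | Section 2.4.4 | Section 4.0, before dosing | Section 5.1, after dosing |
|---|---|---|---|
| Thioridazine | contraindicated | not named; at most read into the phenothiazine entry of exclusion (d), as an anti-emetic, for 48 hours | silent |
| Pimozide | avoid | not named | silent |
| Chronic strong CYP3A4 inducers | avoid | not named | silent |

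Exclusion (a) could reach all three rows, by judgement.

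**Step 2. Timing.** The washout looks back 48 hours. The interaction runs forward at least 7 days, with no stated end. Section 2.4.3 gives a mean half-life of about 170 hours. Assuming simple first-order decay, the fraction of a dose left is 2^(−t/170):

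- at 7 days (168 h): 2^(−168/170) = 0.50
- at 21 days (504 h): 2^(−504/170) = 0.13

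Cycles repeat about every 3 weeks (5.2), and rolapitant may be given for up to 6 cycles (5.5). This arithmetic does not show how long CYP2D6 stays inhibited. It shows only that a rule ending at the first dose does not match the period the protocol itself leaves open.

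**Step 3. The contradiction.** Section 2.4.3 reports raised exposure to dextromethorphan (CYP2D6), digoxin (P-gp) and sulfasalazine (BCRP), and says dose adjustment of sensitive substrates may be needed. Section 2.4.4.1 repeats the inhibition and adds a contraindication. The general statement in 2.4 and 2.4.5 cannot stand beside these. Section 2.4.3 calls the interaction study recent and its results preliminary, so the general statement may simply not have been updated.

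**Step 4. The plan's design figures.** These reproduce.

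- Part I, Section 11 rule (24 then 18 patients; reject at 2 or fewer, then at 8 or fewer). Probability of success = Σ P(X₁ = x)·P(X₂ ≥ 9 − x) for x from 3 to 24, with X₁ ~ Bin(24, p) and X₂ ~ Bin(18, p). At p = 0.11 it is 0.036; at p = 0.32 it is 0.951. Early stopping at 0.11 is P(X₁ ≤ 2) = 0.499, and mean size is 24 + (1 − 0.499) × 18 = 33.0. The plan states limits of 0.05 and 0.05, 50% and 33.
- Part II, 39 per arm, 40% against 11%. Summing both binomials over all tables with two-sided Fisher p ≤ 0.05 gives power 80.2%. The plan states 80%.

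**Step 5. Possible dilution.** The documents give neither the share of patients on strong inducers nor their CR rate. Assume a share f of rolapitant patients takes them and has CR rate c, with Arm B staying at 11%. The rate becomes (1 − f)·p + f·c. For example, at f = 5% and c = 11%, Part II Arm A is 0.95 × 0.40 + 0.05 × 0.11 = 0.3855.

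| f | Part I power, c = 11% | Part I power, c = 0 | Part II power, c = 11% | Part II power, c = 0 |
|---|---|---|---|---|
| 0 | 95.1% | 95.1% | 80.2% | 80.2% |
| 1% | 94.8% | 94.7% | 79.5% | 79.2% |
| 2% | 94.5% | 94.2% | 78.7% | 78.1% |
| 5% | 93.5% | 92.5% | 76.3% | 74.7% |
| 10% | 91.5% | 88.9% | 72.0% | 68.4% |

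**Step 6. Per patient.** One lost response moves the observed rate by 1/39 = 2.6 points in Arm A and 1/42 = 2.4 points in Part I. Those are ceilings, because the patient might not have responded anyway. The expected loss per affected patient is:

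- Arm A: 0.40/39 = 1.0 point if CR falls to 0, or (0.40 − 0.11)/39 = 0.7 if it falls to 11%
- Part I: 0.32/42 = 0.8, or (0.32 − 0.11)/42 = 0.5

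**The case against.** **The rules are silent, not permissive.** A reader might infer that the protocol lets these patients in: that someone on chronic rifampin meets every criterion, or that pausing thioridazine for 48 hours and resuming it on day 2 satisfies the plan. The documents do not support that. Section 2.4.4 is part of the protocol and is worded as instruction, so resuming the drug would breach it. Section 5.1 authorises none of the named drugs. Exclusion (a) fits both cases: a drug said to lower rolapitant's efficacy could confound the result, and a contraindicated one poses a risk. This objection stands. It makes the finding an omission with only a discretionary safeguard, not a permission.

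**The test of rolapitant is hardly weakened.** A reader might also infer that the efficacy comparison is compromised. The thioridazine and pimozide statements concern what rolapitant does to other drugs, and no effect on CR is stated. Only the inducer sentence bears on efficacy, and it gives a direction without a size. A lower rolapitant rate would not raise the chance of a false claim in rolapitant's favour. This also stands.

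**Other documents may cover it.** Section 3.1 requires dispensing under a pharmacy manual, and 2.4.4 cites the prescribing information. Neither is available here, so a check at dispensing cannot be ruled out. It would not remove the inconsistency within the protocol.

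**Investigators may not be misled.** The warnings in 2.4.3 and 2.4.4 are explicit, so any influence of 2.4 and 2.4.5 on their judgement is conjecture. That is fair, but the statements still conflict.

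**Conclusion.** The point holds as a patient-safety inconsistency. Restrictions stated in 2.4.4 are not applied by name in 4.0 or 5.1. The nearest named criterion stops at the first dose, while the protocol describes an interaction lasting at least 7 days. Sections 2.4 and 2.4.5 contradict 2.4.3 and 2.4.4 on whether interactions matter at all. The documents give no frequency; few patients are likely to be affected, but the conflict applies to any one of them.

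The statistical effect is secondary. Under the assumptions in the working, an inducer share of 2% or less costs at most about 1 point of power in Part I and about 2 in Part II. At 5% the loss is about 2 to 3 points in Part I and 4 to 6 in Part II; at 10% it is about 4 to 6 and 8 to 12. These figures assume that inducers leave Arm B at 11%, on which the documents are silent. Any dilution would work against rolapitant. The planned sizes of 42 and 39 per arm are not in question.

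**What to change.** The study team should:

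- Reconcile Sections 4.0 and 5.1 with the restrictions already stated in 2.4.4, for the whole period in which the protocol says the interaction may persist. Since 2.4.4.1 gives no end to that period, the team should state the period it uses and why.
- Keep eligibility the same for both Part II arms, so that any criterion is applied before randomization and the arms stay comparable.
- Correct the general statements on interactions in 2.4 and 2.4.5 to agree with 2.4.3 and 2.4.4.

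The exact criteria and durations are clinical decisions for the study team; none is proposed here.

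The cost is protocol wording, a medication check at screening and a very small loss of eligible patients. Sample sizes, decision rules and analyses stay as they are.
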